 - Laboratory (including but not limited to CBC, TSH, electrolytes)

Study Population

Inclusion Criteria

- Age 18+
- Meets WHO-defined post-COVID-19 condition
 - WHO definition: 'Post COVID-19 condition occurs in individuals with a history of probable or confirmed SARS-CoV-2 infection, usually 3 months from the onset of

COVID-19 with symptoms that last for at least 2 months and cannot be explained by an alternative diagnosis. Common symptoms include fatigue, shortness of breath, cognitive dysfunction but also others and generally have an impact on everyday functioning. Symptoms may be new onset following initial recovery from an acute COVID-19 episode or persist from the initial illness. Symptoms may also fluctuate or relapse over time.⁶

- To ensure the above criteria is met, participants will only be included in the study if they meet all eligibility criteria more than 12 weeks from their confirmed and documented positive polymerase chain reaction (PCR) SARS-CoV-2 test, rapid antigen, or antibody test. In lieu of a prior positive test, a signed confirmation of a presumptive prior COVID-19 case from a healthcare provider, including the study physician, is acceptable.
- Documented history of SARS-CoV-2 infection with typical symptoms, and requiring positive SARS-CoV-2 test (PCR, antigen, or serology) at some point during the course of the acute course of illness. In lieu of a prior positive test, a confirmation of a presumptive prior COVID-19 case from a healthcare provider, including the study physician, is acceptable.
- Subjective cognitive complaints as detected by the Perceived Deficits Questionnaire (PDQ)-5.
- Ability to provide written informed consent.
- Resident of Canada.

Exclusion Criteria

- Current symptoms are fully explained by major depressive disorder or bipolar disorder.
- Pre-existing conditions that may cause cognitive impairment, or symptoms similar to those seen in post-COVID-19 condition (e.g., ADHD, major neurocognitive disorder, schizophrenia, chronic fatigue syndrome [CFS]/ encephalitis meningitis [EM]), as assessed by Mini International Neuropsychiatric Interview (MINI) 7.0.2.
- Inability to follow study procedures.
- Known intolerance to vortioxetine and/or prior trial of vortioxetine with demonstrated inefficacy.
- If participants are currently taking other antidepressants, they will be asked to discontinue the antidepressant for 2-4 weeks in order to participate in the study.

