- Patients on other antidepressants are allowed to participate only if the antidepressant is prescribed at subtherapeutic doses for a primary indication other than mood disorders. Participants will be made aware in the consent form that the combination of the two antidepressants would be considered investigational and that the safety/efficacy profiles are unknown ²⁸⁻³⁰.
- Current alcohol or substance use disorder.
- Inability to provide consent.
- Current alcohol and/or substance use disorder as confirmed by the M.I.N.I 7.0.2.
- Presence of comorbid psychiatric disorder that is a primary focus of clinical concern as confirmed by the M.I.N.I. 7.0.2.
- Medications approved and/or employed off-label for cognitive dysfunction (e.g., psychostimulants).

- Any medication for a general medical disorder that, in the opinion of the investigator, may affect cognitive function.
- Use of benzodiazepines within 12 hours of cognitive assessments.
- Consumption of alcohol within 8 hours of cognitive assessments.
- Physical, cognitive, or language impairments sufficient to adversely affect data derived from cognitive assessments.
- Diagnosed reading disability or dyslexia.
- Clinically significant learning disorder by history.
- Electroconvulsive therapy (ECT) in the last 6 months.
- History of moderate or severe head trauma (e.g., loss of consciousness for >1 hour), other neurological disorders, or unstable systemic medical diseases that in the opinion of the investigator are likely to affect the central nervous system.
- Pregnant and/or breastfeeding.
- Received investigational agents as part of a separate study within 30 days of the screening visit.
- Actively suicidal/presence of suicidal ideation or evaluated as being at suicide risk (as per clinical judgment).
- Currently receiving treatment with Monoamine Oxidase Inhibitors (MAOIs) antidepressants, antibiotics such as linezolid, or intravenous methylene blue.
- Previous hypersensitivity reaction to vortioxetine or any components of the formulation. Angioedema has been reported in patients treated with vortioxetine.
- Serotonin syndrome.
- Abnormal bleeding.
- Previous history of mania/hypomania.
- Angle closure glaucoma.
- Hyponatremia.
- Moderate hepatic impairment.
- Active seizure disorder/epilepsy, not controlled by medication (per study physician assessment).
- Presence of any unstable medical conditions.

Recruitment

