Recruitment will take place via media announcements (e.g., print, social media, public broadcasting stations). Announcement of study recruitment will also be provided to primary health care providers in Canada.

Study Visits

Study visits may be conducted remotely (e.g. zoom), by telephone or in-person. Visits with the study physician will primarily occur via a secure online platform (e.g. OTN) or by telephone. If required/requested, in-person visits with the study physician may be scheduled.

Participants may be emailed a secure, unique and anonymized RedCap link to complete self-report questions at home within 24 hours of their scheduled visit (before or after visit). This is to reduce participant burden during the visit with research staff/study physicians. Participants will

be asked to complete self-report questionnaires at the same time block of the day during all study visits (i.e. all mornings, afternoons or evenings).

Pre-Screen

Participants will be pre-screened via telephone, email, or an online form to determine if they meet above noted inclusion and exclusion criteria.

Screening Visit (Visit 0)

Once participants provide written, informed consent, they will undergo a comprehensive assessment to determine eligibility during the screening visit. Details of assessments completed are included in Table 1.

Baseline (Visit 1)

Participants will undergo the various assessments listed in Table 1. In addition, participants will have their blood drawn and may be invited to participate in an optional fMRI scan (see details below). Participants will also be assessed by a study physician at one time point between the screening and baseline visits and be provided a prescription for vortioxetine. Research staff (i.e. research coordinators/research assistants) will dispense the medication to the participant based on the direction from the study physician/prescription from the study physician for the first two weeks of the study. For remote participants, research staff will mail medication for the first two weeks of the study with appropriate temperature monitoring.

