Week 2 (Visit 2): Participants will complete items listed in Table 1, Week 2 (Visit 2). The study physician will determine if the participant is eligible for a dose increase. Research staff (i.e. research coordinators/research assistants) will dispense medication to the participant based on the direction from the study physician/prescription from the study physician for the next six weeks of the study. For remote participants, medication for the remaining six weeks of the study will be mailed out as well as medication for discontinuation by research staff with appropriate temperature monitoring.

Week 4 (Visit 3): Participants will complete items listed in Table 1, Week 4 (Visit 3).

Week 8 (Visit 4): Participants will complete items listed in Week 8 (Visit 4). The study physician will also discuss transition of care (see below) and/or medication continuation. Participants will also have their blood drawn and may be asked to participate in the optional fMRI scan.

Optional Post-Study (Week 10): Clinical visit with physician if the participant is discontinuing the study medication and/or as needed. If a participant chooses to continue with the study medication, he/she will be asked to follow up with his/her most responsible physician (MRP) for ongoing care and this post-study visit would not be needed. Participants will be informed prior to signing the consent form that research staff/research physician will not be able to tell them if they received drug or placebo when they finish the study at week 8 and they will have to wait until the entire study is complete to find out.

Table 1. Study schedule with assessments

Study Visit	Screening (Visit 0)	Baseline (Visit 1)	Visit 2	Visit 3	End-of-study (Visit 4)
Week	(-1 to -21 days from baseline)	0	2 (+/- 2 days)	4 (+/- 2 days)	8 (+/- 2 days)
Consent	X				
Inclusion/Exclusion	X				
Demographics	X				
Past COVID-19 Infection Information	X				

M.I.N.I 7.0.2	X				
Psychiatric/Medical History	X				
Lifestyle Factors	X				
Current Medications	X	X	X	X	X
Medication Changes	X	X	X	X	X
Adverse Events		X	X	X	X
Anthropometrics		X	X		X
MoCA		X			
SETS		X			
DSST		X	X		X
TMT-A/B		X	X		X
RAVLT		X	X		X
CogState Online Cognitive Battery**		X	X		X
PDQ-20		X	X	X	X
GAD-7		X	X	X	X
SHAPS		X	X	X	X
FSS		X	X	X	X
WHO-5		X	X	X	X
SDS		X	X	X	X
BAS		X	X	X	X
EQ-5D-5L		X	X	X	X
QIDS-SR16		X	X	X	X
IPAQ		X		X	X
PCFS	X	X	X	X	X
EEfRT		X			X

Physician Assessment*	X		X	X	X
Laboratory assessments		X			X
fMRI + Cognitive Test		X			X

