Abbreviations: ^a: BAS: Behavioural Activation Scale; DSST: Digit Symbol Substitution Test; EQ-5D-5L: 5-Level EQ-5D version; fMRI: functional magnetic resonance imaging; FSS: Fatigue Severity Scale; GAD-7: Generalized Anxiety Disorder, 7-item; IPAQ: International Physical Activity Questionnaire; EEfRT: Effort Expenditure for Rewards Task ; M.I.N.I: Mini-International Neuropsychiatric Interview; MoCA: Montreal Cognitive Assessment; PCFS: Post-Covid Functional Scale; PDQ-20: Perceived Deficits Questionnaire, 20-item; Quick Inventory of Depressive Symptomatology (16-Item) (Self-Report) (QIDS-SR16); RAVLT: Rey's auditory verbal learning test; RPE: Borg Rating of Perceived Exertion Scale; SDS: Sheehan Disability Scale; SETS: Stanford Expectations of Treatment Scale; SHAPS: Snaith-Hamilton Pleasure Scale; TMT-A/B: Trails Making Test-A/B; WHO-5: World Health Organization Well-Being Index, 5-item.

*One physician assessment will be conducted between the baseline and screening visit.

**May be conducted remotely.

Sample Size

- Total recruitment N=200 (i.e., 100 subjects allocated to vortioxetine [5-20 mg] and placebo each).
- The target sample size is based on effect sizes reported by previous clinical trials that evaluated the efficacy of antidepressants vs placebo and nutraceuticals in individuals with chronic fatigue syndrome ^{6,23-25}.
- The effect size of vortioxetine on DSST-measured cognitive function is estimated at approximately 0.2-0.5 ^{26,27}. Previous experience without patients enrolled in clinical trials (investigator-initiated trials) with vortioxetine as part of the THINC-it tool validation indicated that vortioxetine improves measures of processing speed (the prominent domain validated by the DSST) of significance with a sample size of 200.
- It is then estimated that a sample size of 100 per treatment arm would detect clinically relevant change with vortioxetine treatment on DSST as the dependent measure ^{27,31}.

Feasibility

- It is estimated, based on prior general population research conducted by the BCDF, that recruitment will take approximately 12 months.
- Community research ethics board approval, 2-4 weeks (BCDF is an independent research center not requiring university- or hospital-based REB reviews).

Description of Study Procedures

Efficacy Assessments

Digit Symbol Substitution Test (DSST)

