- Hemorrhage (including contusion, ecchymosis, epistaxis, gastrointestinal or vaginal hemorrhage)

Please see product monograph for full details.

Contraindications

Hypersensitivity to vortioxetine or any components of the formulation. Angioedema has been reported in patients treated with vortioxetine. The use of monoamine oxidase inhibitors (MAOI) intended to treat psychiatric disorders with vortioxetine or within 21 days of stopping treatment with vortioxetine is contraindicated because of an increased risk of serotonin syndrome. The use of vortioxetine within 14 days of stopping an MAOI intended to treat psychiatric disorders is also contraindicated.

Starting vortioxetine in a patient who is being treated with MAOIs or antibiotics such as linezolid or intravenous methylene blue is also contraindicated because of an increased risk of serotonin syndrome.

Storage

Medication will be stored at room temperature in a locked cabinet and office space at BCDF ([name]).

Transition to Standard of Care

Patients will be informed of the transition to standard of care procedures (outlined here) post study prior to providing consent to participate in the study. These procedures will also be outlined in writing in the patient consent form itself.

Upon completing the 8-week course of vortioxetine, if patients benefit from this drug, they will be encouraged to continue the treatment with their most responsible physician (MRP). Patients will be notified prior to study consent that not all drug plans will cover the cost of vortioxetine. Should patients wish to continue to use this drug post-study when they do not have coverage, they will be personally responsible for the costs.

If patients do experience side effects during the study, the study physician will make a recommendation regarding the discontinuation or dose reduction of the medication for the

remainder of the study. If participants do not experience any improvement upon study completion in mood or cognition, the medication will be gradually discontinued over a two-week period upon study completion (end of week 8). Participants will take half of their final dose of vortioxetine during the first week post-study and no medication during the second week of discontinuation. Participants will be provided with one week worth of medication for this discontinuation process but will not be provided any further supply thereafter.

Vortioxetine discontinuation process

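### The MAOI exclusion covers current use only and omits the protocol's own 14-day window after stopping an MAOI

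*Combined protocol and SAP*

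**What the plan says.** Study Population, Exclusion Criteria, bars people "Currently receiving treatment with Monoamine Oxidase Inhibitors (MAOIs) antidepressants, antibiotics such as linezolid, or intravenous methylene blue". This is a current-use test with no look-back.

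The Contraindications section, under the study medication, covers two MAOI situations that matter at entry. One is starting vortioxetine in someone being treated with an MAOI, linezolid or intravenous methylene blue; the exclusion mirrors this. The other is recent use: "The use of vortioxetine within 14 days of stopping an MAOI intended to treat psychiatric disorders is also contraindicated". The section gives an increased risk of serotonin syndrome as the reason for its MAOI contraindications.

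Other provisions bear on the same person:

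- Exclusion Criteria, other antidepressants: "If participants are currently taking other antidepressants, they will be asked to discontinue the antidepressant for 2-4 weeks".
- Pre-Screen: "Participants will be pre-screened via telephone, email, or an online form to determine if they meet above noted inclusion and exclusion criteria".
- Exclusion Criteria, psychiatric comorbidity: "Presence of comorbid psychiatric disorder that is a primary focus of clinical concern as confirmed by the M.I.N.I. 7.0.2".
- Baseline (Visit 1): each participant is to be "assessed by a study physician at one time point between the screening and baseline visits and be provided a prescription for vortioxetine".
- Table 1: screening is placed at minus "1 to -21 days from baseline". Psychiatric and medical history is taken at screening; current medications and medication changes are recorded at both screening and baseline.

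**The concern.** Eligibility criteria are what staff apply and document. Here the entry rule is looser than the safety rule in the same protocol. Someone who has recently stopped a psychiatric MAOI is no longer a current user, so neither the MAOI exclusion nor the discontinuation rule applies, yet for 14 days that person must not be given vortioxetine.

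The omission is not a matter of drafting style. The same list sets look-backs for ECT (6 months), investigational agents (30 days), benzodiazepines (12 hours before cognitive testing) and alcohol (8 hours before cognitive testing). The post-MAOI window, which the protocol itself makes a contraindication, is absent.

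What is at stake is participant safety. Only the vortioxetine arm is exposed, but the trial is double-blind, so the check has to be made for everyone before the first dose. The efficacy analysis is not affected.

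**Working it through.** The plan gives no figure to reproduce. The check compares the text and then counts days.

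**Text comparison**

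| Situation at first dose | Contraindications section | Exclusion Criteria |
|---|---|---|
| Currently on an MAOI, linezolid or IV methylene blue | Contraindicated | Excluded |
| Stopped a psychiatric MAOI within 14 days | Contraindicated | No criterion |
| Stopped linezolid or IV methylene blue recently | No window stated | No criterion (consistent) |

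Only the second row is in conflict.

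**Do other provisions close it?**

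- The discontinuation rule is triggered by current antidepressant use. Its lower limit of 2 weeks is 14 days, so it just reaches the window for people who stop in order to join. It does not reach those who had already stopped.
- Pre-screening catches a person still on an MAOI at that point. It applies the same criteria, so it also lacks the window.
- The psychiatric comorbidity exclusion applies only where the disorder is the main clinical concern. It may catch some of these people.
- The schedule allows baseline 1 day after screening, so elapsed time does not guarantee 14 days.

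**Day count**

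Inputs from the documents: window of 14 days (Contraindications); screening-to-baseline interval *s* of 1 to 21 days (Table 1).

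Assumptions: the MAOI was stopped 1 day before pre-screening; pre-screening to screening takes *g* days (not stated in the documents); first dose is on the baseline day.

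Days from stopping to first dose = 1 + *g* + *s*. The window is open while 1 + *g* + *s* ≤ 14, or ≤ 13 if day 14 is read as outside.

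| Assumed *g* | Open *s*, day 14 inside | Open *s*, day 14 outside |
|---|---|---|
| 0 | 1-13 | 1-12 |
| 3 | 1-10 | 1-9 |
| 7 | 1-6 | 1-5 |

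With the shortest interval, *s* = 1, the window closes once 1 + *g* + 1 exceeds the limit: *g* ≥ 13 with day 14 inside, *g* ≥ 12 with it outside.

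Extreme case, *g* = 0 and *s* = 1: first dose falls 1 + 0 + 1 = 2 days after stopping.

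**Share exposed**

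Sample Size plans "Total recruitment N=200 (i.e., 100 subjects allocated to vortioxetine [5-20 mg] and placebo each", so 100/200 = 0.5. On average half of any such participants would receive active drug.

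**The case against.** The strongest reply is that the protection already exists. The 14-day rule is operative protocol text, a physician bound by it assesses every participant and writes the prescription, and staff dispense only on that direction. Table 1 collects the history and medication fields in which a recently stopped MAOI should appear. On this view the rule is merely missing from one list, and the group left over is thin: someone with a treated psychiatric illness, who stopped on their own just before contact, who is not caught by the psychiatric exclusions, and whose recent MAOI use went undisclosed or was overlooked by the physician. The day counts also rest on stacked assumptions, and mailing the drug to remote participants could push the first dose later.

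Much of this stands. The physician is a real safeguard, the group is probably very small, and the day counts bound timing without measuring risk. What does not follow is that nothing needs changing. No procedure asks for an MAOI stop date, Table 1 sets no look-back for medication changes, and no criterion says what to do if a recent stop is found. Protection therefore depends on the physician recalling a rule from another section, when a listed criterion would make the check explicit and documented.

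**Conclusion.** The concern holds. The eligibility rule passes a person whom the protocol's own contraindication says must not be dosed, and no other listed criterion or scheduled interval reliably prevents it. The practical size is small: probably very few people, with no count available and none estimated. In the least favourable case, 13 of the 21 permitted screening-to-baseline intervals leave the window open (12 if day 14 is outside). That is an upper bound resting on the stop date, pre-screen timing and first-dose day assumed above.

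This is an inexpensive safety correction that should be made, with moderate confidence in its practical weight given the physician assessment.

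**What to change.** Replace the MAOI exclusion with wording to this effect:

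> Stopped an MAOI given for a psychiatric disorder within 14 days before the first dose of study medication; or currently taking any MAOI, linezolid or a similar antibiotic, or IV methylene blue.

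Have the study physician confirm and record the MAOI stop date at the assessment already scheduled before baseline.

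Two features of the wording are deliberate. The look-back stays limited to psychiatric MAOIs and adds no window for linezolid or methylene blue, as in the Contraindications section. The current-use part says any MAOI, which is slightly broader than the present reference to MAOI antidepressants but matches that section's general concurrent-use rule.

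The cost is one line and one date. A few candidates would wait. Someone who stopped the day before screening could be dosed from day 14 after screening, since 1 + 14 = 15 exceeds 14; that is 14 − 1 = 13 days later than the shortest permitted interval. If day 14 is outside the window, the figures are day 13 and 12 days. Both fall inside the 21-day screening window, so rescreening should rarely be needed.

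### The MAOI exclusion covers current use only, although the protocol also contraindicates vortioxetine within 14 days of stopping an MAOI

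*Combined protocol and SAP*

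**What the plan says.** The MAOI line in Study Population, Exclusion Criteria covers anyone "Currently receiving treatment with Monoamine Oxidase Inhibitors (MAOIs) antidepressants, antibiotics such as linezolid, or intravenous methylene blue". It is in the present tense and carries no look-back.

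The Contraindications section, placed with the drug information, has two rules that bear on starting vortioxetine:

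- Concurrent treatment: "Starting vortioxetine in a patient who is being treated with MAOIs or antibiotics such as linezolid or intravenous methylene blue is also contraindicated".
- Recent treatment: "The use of vortioxetine within 14 days of stopping an MAOI intended to treat psychiatric disorders is also contraindicated".

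Three other provisions matter:

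- An antidepressant washout appears in the exclusion list: "If participants are currently taking other antidepressants, they will be asked to discontinue the antidepressant for 2-4 weeks".
- Table 1 places screening 1 to 21 days before baseline and marks the inclusion/exclusion check at screening only.
- Under Baseline (Visit 1), participants are to be "assessed by a study physician at one time point between the screening and baseline visits and be provided a prescription for vortioxetine".

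**The concern.** Of the two rules on starting vortioxetine around MAOI use, the exclusion list carries over only the one on concurrent treatment. Someone who stopped an MAOI a few days before screening is no longer receiving it, so the written criteria pass them, yet the protocol's own drug section says they must not be dosed.

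The omission does not look deliberate. The list uses look-back windows elsewhere, for example "Received investigational agents as part of a separate study within 30 days of the screening visit", and no reason is given for leaving this one out.

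What is at stake is participant safety. The sentences on MAOIs around the 14-day rule give a raised risk of serotonin syndrome as their reason, and participants aged 18-64 start at 10 mg/day. Because the trial is blinded, everyone randomized must be fit to receive the active drug. Power, type I error and the primary analysis are not affected.

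**Working it through.** The plan states no figure to reproduce. The check compares the text and then counts days.

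**Side by side**

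| Situation at study entry | Contraindications section | Exclusion criteria |
|---|---|---|
| On an MAOI now | Contraindicated | Excluded |
| Stopped a psychiatric MAOI less than 14 days ago | Contraindicated | Not addressed |
| On linezolid-type antibiotics or IV methylene blue now | Contraindicated | Excluded |
| Recently stopped linezolid-type antibiotics or IV methylene blue | No interval given | Not addressed |

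The mismatch is confined to the second row.

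**Does the washout close it?** It applies to people currently taking an antidepressant. Someone who stops an MAOI in order to enter and completes 2-4 weeks has been off it for 14-28 days, which satisfies the rule. Someone who had already stopped before screening falls outside its wording.

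**Day count**

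Inputs:
- s = days since the last MAOI dose at screening (not in the documents, so varied below)
- g = days from screening to baseline, 1 to 21 (Table 1)
- required time off = 14 days (Contraindications)
- assumption: first dose on the baseline day

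Time off at first dose is T = s + g. The person is eligible but contraindicated when s + g < 14, that is, when g ≤ 13 − s. For s from 1 to 12, the number of permitted values of g that leave the gap open is therefore 13 − s.

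| s | Shortest T (g = 1) | Shortfall from 14 | Values of g that leave the gap open | Share of the 21 |
|---|---|---|---|---|
| 1 | 2 days | 12 days | 1-12 (12) | 12/21 = 57% |
| 7 | 8 days | 6 days | 1-6 (6) | 6/21 = 29% |
| 12 | 13 days | 1 day | 1 (1) | 1/21 = 5% |
| 13 | 14 days | 0 | none | 0 |

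The s = 1 row takes current use to end the day after the last dose. The s = 7 row shows a looser reading, under which a person counts as a current user for a week; the documents support neither reading over the other.

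**After the correction.** With use in the 14 days before first dose excluded, T is at least 14 whatever g is. For s = 1, the earliest compliant baseline is 14 − 1 = 13 days after screening, inside the 21-day window.

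**The case against.** The strongest reply is that the 14-day rule is already in the protocol, only in another section, and that several steps could enforce it. A physician must assess each participant and prescribe before baseline. Psychiatric and medical history is taken at screening, and current medications and medication changes are recorded at screening and at baseline. Participants are also pre-screened against the same criteria, so a person who passes both checks has usually been off the MAOI since before pre-screening. The remaining group is narrow: people who stopped a psychiatric MAOI for their own reasons shortly before contacting the study, and who also pass the other psychiatric exclusions. Half of participants receive placebo, so a recent stopper who is admitted has about a 50% chance of never taking vortioxetine. Finally, the percentages count calendar intervals and are not risks.

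Much of this stands as context. The group is probably small, the percentages must not be read as probabilities of harm, and a careful physician would be likely to stop the dose. For remote participants, mailed medication could also put the first dose after baseline and lengthen the time off.

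None of it closes the gap. Pre-screening applies the same incomplete criteria, and no minimum interval separates it from screening. The medication and history items carry no decision rule and do not ask for the date of the last MAOI dose. The physician's assessment is not tied to the 14-day rule. Placebo allocation halves the exposure of a person wrongly admitted but does not make that person eligible.

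**Conclusion.** The concern holds. As written, the eligibility criteria can admit a participant for whom the first dose of vortioxetine is contraindicated by the protocol itself. In the worst case counted here, the dose comes 2 days after stopping an MAOI instead of at least 14. For that person, 12 of the 21 permitted screening intervals leave the gap open; by s = 13 none do.

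This rests on the first dose being taken on the baseline day and on current use ending the day after the last MAOI dose. The number of participants affected is unknown. It is a gap in the eligibility wording, not evidence that a contraindicated dose would be given. It is limited to MAOIs taken for psychiatric disorders and does not extend to linezolid-type antibiotics or methylene blue.

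**What to change.** Amend the MAOI part of the exclusion line to read: *currently receiving an MAOI, or took an MAOI for a psychiatric disorder within 14 days before the first dose of study medication*. Leave the parts on antibiotics and methylene blue as they are.

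To make the rule enforceable:

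- Record the date of the last MAOI dose under the existing medication items at screening.
- Have the study physician confirm, before issuing the prescription, that at least 14 days will have passed by the planned first dose.
- If the interval is too short, move baseline later within the 21-day window.

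The cost is one edited line and one date collected at a visit already scheduled. The longest delay, for a last dose 1 day before screening, is 13 − 1 = 12 days beyond the earliest permitted baseline. No one need be lost for this reason alone, and the visits, sample size and analysis stay the same.

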Laboratory Assessment: Participants will be asked to fast for 8 hours prior to their baseline (visit 1) and week 8 (visit 4). Participants will have blood drawn for standard clinical parameters. These include glucose, insulin, electrolytes, liver and kidney function tests, lipids, CBC, inflammatory markers (e.g. CRP, ESR), albumin and protein. Participants may also have their blood drawn for various exploratory secondary analyses (e.g. cytokines). Approximately 20 mL of blood will be drawn in 4-5 blood tubes. Two of these tubes will include lavender tubes with EDTA for exploratory analyses. A urine or blood pregnancy test will be conducted for all female participants.

Remote participants will be provided a blood requisition form via email or mail to have clinical blood drawn and analyzed at the participant's local blood lab facility. Blood will not be collected for exploratory purposes from remote participants. Female participants may provide a blood or urine sample to the local blood lab to confirm non-pregnancy. Participants may also be mailed a home pregnancy test.

Exploratory Blood Analyses: For participants seen in-person, they will be able to volunteer to provide a blood sample for exploratory analyses. The sample will be collected at a local blood lab (e.g. Mount Sinai Hospital), followed by processing and storage of the sample at the Biospecimen Repository and Processing Lab (Lunenfeld-Tanenbaum Research Institute, Sinai Health). Participants may also have blood drawn at the same time for clinical purposes at Mount Sinai Hospital. The clinical blood tubes will be delivered to another local lab (e.g. Dynacare, LifeLabs) for analyses. Alternatively, participants may also have blood drawn separately for clinical analyses at a local blood lab near them - this will result in two separate blood draws.

fMRI: A subset of participants may be offered the opportunity to have an fMRI scan completed at baseline and endpoint for secondary, exploratory purposes. This is optional and not the primary focus of the study. Participants may still participate in the study and decide not to participate in this component. During the imaging, participants will be asked to complete a cognitive task (e.g. Effort Expenditure for Rewards Task, Trails Making Test A/B). Participants will be awarded the amount of money they earn during this task, on top of the standard compensation to all participants. Please see “Participant Compensation” for more details.

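### The only liver exclusion names the moderate grade and, read literally, leaves severe hepatic impairment eligible

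*Combined protocol and SAP*

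**What the plan says.** In the protocol, Study Population, Exclusion Criteria, the hepatic criterion reads in full "Moderate hepatic impairment". Two broader exclusions in the same list could touch liver disease: "Presence of any unstable medical conditions", and a neurological and systemic bullet that ends with "unstable systemic medical diseases that in the opinion of the investigator are likely to affect the central nervous system".

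Eligibility is first checked remotely. Under Pre-Screen: "Participants will be pre-screened via telephone, email, or an online form to determine if they meet above noted inclusion and exclusion criteria". Table 1 marks the inclusion/exclusion check, psychiatric and medical history, and current medications at the screening visit. Under Baseline (Visit 1): "Participants will also be assessed by a study physician at one time point between the screening and baseline visits". That physician also provides the prescription.

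The Laboratory Assessment paragraph includes "liver and kidney function tests" among the blood tests at baseline and week 8. The Contraindications section opens with "Hypersensitivity to vortioxetine or any components of the formulation" and goes on to monoamine oxidase inhibitors, linezolid and intravenous methylene blue. It does not mention the liver.

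**The concern.** Severity grades are ordered, and a safety exclusion that bars one grade should bar every worse grade. This one names only the middle grade. Someone applying the list as written would exclude a person with moderate impairment and would find no line that excludes a person with severe impairment, which is the wrong way round for a safety rule.

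The exact wording matters more here than in a trial where a clinician applies every criterion face to face. The criteria are first applied by telephone, email or online form, physician visits are mainly online or by telephone, and people may take part entirely remotely and receive the drug by mail. What is at stake is the safety of a participant who should not have been dosed. No estimate or test in the analysis depends on this line.

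**Working it through.** No power, error-rate or sample-size calculation applies. The check is a count of the exclusion list, followed by a comparison of every line that could exclude severe hepatic impairment by another route.

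**Count.** The exclusion list has 32 bullets. One names the liver, and it names one grade.

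**How the list writes two grades elsewhere.** The head-trauma exclusion spells out both the moderate and the severe grade. The hepatic line does not follow that style, which points to a drafting slip and not to a decision to admit severe disease.

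**Other routes to exclusion.**

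| Place in the protocol | What it covers | Does it exclude stable severe hepatic impairment? |
|---|---|---|
| Exclusion: "Presence of any unstable medical conditions" | Unstable disease of any kind | No; it requires instability |
| Exclusion: "unstable systemic medical diseases that in the opinion of the investigator are likely to affect the central nervous system" | Unstable disease with a likely central nervous system effect | No; it requires instability and a likely CNS effect |
| Exclusions for abnormal bleeding and for hyponatremia | Those findings only | Some cases, not the condition |
| Exclusion for pre-existing conditions that may impair cognition | Assessed by the MINI, a psychiatric interview | Some cases, not the condition |
| Contraindications | Hypersensitivity, MAOIs, linezolid, methylene blue | No hepatic entry |
| Laboratory Assessment: "liver and kidney function tests" | Baseline and week 8 | No threshold for entry |
| Clinical Laboratory Tests (Safety Assessments) | Routine list | Names no liver test |
| Clinical Laboratory Changes | Total bilirubin at least 2 × ULN with ALT or AST at least 3 × ULN | No; this triggers adverse-event reporting |

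**Timing of the liver tests.** Table 1 places the inclusion/exclusion check at screening and the laboratory assessments at baseline and week 8. The schedule therefore puts the liver tests after the marked eligibility check, and no rule says that the results must be reviewed before dosing.

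**Exposure.** The Sample Size section has "100 subjects allocated to vortioxetine [5-20 mg] and placebo each". If anyone with severe impairment were enrolled, 100/200 = 50% of such people would be expected on placebo. This halves an already small number but does not estimate it. The documents give no prevalence from which to do so.

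**The case against.** The strongest reply is that no sensible reader would take a safety list to bar a milder grade and admit a worse one, and that nothing in the protocol permits severe impairment. Further lines also narrow the gap. Inclusion follows the WHO definition, under which symptoms must not have another explanation, and severe liver disease could be such an explanation for fatigue or cognitive complaints. Drugs for a general medical disorder that the investigator thinks may affect cognition are an exclusion. A physician sees every participant before baseline. The protocol refers to the product monograph for full details, so the short Contraindications section need not be complete. Finally, the documents do not say how hepatic impairment alters exposure to vortioxetine or its risk.

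Most of this stands, and it is why the point is minor. These safeguards make it unlikely that anyone with severe impairment would be dosed. They do not correct the criterion: each depends on someone supplying words that the line omits, or on a feature that stable severe disease may not show. Nor is pharmacological evidence needed to make the point. The protocol itself treats moderate impairment as disqualifying, and the more severe grade should follow.

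**Conclusion.** The concern holds. The criterion is wrong as written: taken literally, it excludes the moderate grade and does not exclude the severe one, and no other line does so by name or by threshold. This is a minor safety wording error. The number of participants affected cannot be derived from the documents and is probably very small. There is no effect on power, type I error or the primary analysis.

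The conclusion rests on a literal reading of the list and on the assumption that the intended rule is moderate or worse. It uses no product-label information from outside the documents. Confidence is high about the text. The documents do not allow any estimate of harm.

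**What to change.** Change the bullet to *Moderate or severe hepatic impairment*. The sponsor's medical lead should confirm that this is the intended scope. Use the same wording in the pre-screen form, at the screening visit and in the study physician's assessment.

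The cost is a few words in the exclusion list, with a negligible effect on recruitment and none on the sample size or the analysis.
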